1. PROTOCOL SUMMARY

1.1. Synopsis

A Randomized, Double-blind, Placebo-controlled Phase 2a Study to Evaluate a Range of Dose Levels of an Ad26.RSV.preF-based Vaccine in Adults Aged 60 Years and Older

The respiratory syncytial virus (RSV) vaccine that will be investigated in the current study, the Ad26/protein preF RSV vaccine (VAC18193), is a combination of 2 vaccine components, administered as a single intramuscular (IM) injection:

- Ad26.RSV.preF (JNJ-64400141), a replication-incompetent adenovirus serotype 26 (Ad26) containing a DNA transgene that encodes the prefusion conformation-stabilized F protein (preF) derived from the RSV A2 strain.
- RSV preF protein (JNJ-64213175), a recombinant preF protein derived from the RSV A2 strain.

The aim of this dose-ranging study is to determine the safety and immunogenicity of different dose levels of Ad26.RSV.preF in the Ad26/protein preF RSV vaccine to support the refinement of the acceptance criteria for drug product release and stability by generating additional information on clinical safety (for the upper release limit) and immunogenicity (for the lower release limit).

OBJECTIVES AND ENDPOINTS

Objectives	Endpoints
Cohort 1	
Primary	

 • To explore the dose-response relationship of humoral immune responses induced by different dose levels of the Ad26.RSV.preF-based vaccine 	
 • Antibody titers to RSV preF protein using preF enzyme-linked immunosorbent assay (ELISA) at 14 days after vaccination
Secondary	

 • To explore the dose-response relationship of humoral and cellular immune responses induced by different dose levels of the Ad26.RSV.preF-based vaccine 	
 • Antibody titers to RSV preF protein using preF ELISA at 3 and 6 months after vaccination • RSV A2 neutralizing antibody levels at 14 days and 3 and 6 months after vaccination • Interferon (IFN)-γ enzyme-linked immunospot (ELISpot) assay at 14 days and 3 and 6 months after vaccination

 • To assess the safety and reactogenicity of different dose levels of the Ad26.RSV.preF-based vaccine 	
 • Serious adverse events (SAEs) from the time of vaccination until the end of the study • Solicited local and systemic adverse events (AEs) from the time of vaccination until 7 days after vaccination • Unsolicited AEs from the time of vaccination until 28 days after vaccination

Objectives	Endpoints
Cohort 1	
Exploratory	

 To explore additional vaccine-elicited immune responses 	
Assays that may be used include, but are not limited to:
 
 Post-F protein binding antibodies (ELISA) Antigen-specific T-cell immune responses RSV cross-neutralization of B and/or other A strain(s) Anti-F protein antibody specificity characterization Analysis of immunoglobulin (Ig)A and/or IgG antibodies binding to RSV F protein in prefusion and/or postfusion form in nasal samples Analysis of neutralizing antibodies to Ad26
Objectives	
Cohorts 2 and 3	
Primary	

 To assess the safety and reactogenicity of different dose levels of the Ad26.RSV.preF-based vaccine 	
 Solicited local and systemic AEs from the time of vaccination until 7 days after vaccination Unsolicited AEs from the time of vaccination until 28 days after vaccination
Secondary	

 To assess the humoral and cellular immune responses induced by different dose levels of the Ad26.RSV.preF-based vaccine 	
 Antibody titers to RSV preF protein using preF ELISA at 14 days and 3 and 6 months after vaccination RSV A2 neutralizing antibody levels at 14 days and 3 and 6 months after vaccination IFN-γ ELISpot assay at 14 days and 3 and 6 months after vaccination

 To assess the safety of different dose levels of the Ad26.RSV.preF-based vaccine 	
 SAEs from the time of vaccination until the end of the study
Exploratory	

 To explore additional vaccine-elicited immune responses 	
Assays that may be used include, but are not limited to:
 
 Post-F protein binding antibodies (ELISA) Antigen-specific T-cell immune responses RSV cross-neutralization of B and/or other A strain(s)

	
 Anti-F protein antibody specificity characterization Analysis of IgA and/or IgG antibodies binding to RSV F protein in prefusion and/or postfusion form in nasal samples Analysis of neutralizing antibodies to Ad26
--	--

Hypothesis

No formal statistical testing of safety or immunogenicity data is planned; data will be analyzed descriptively.

OVERALL DESIGN

This is a randomized, double-blind, placebo-controlled, multicenter, interventional Phase 2a study in male and female adults aged ≥ 60 years who are in stable health, to explore the dose-response relationship, safety, and immunogenicity of a range of dose levels of the Ad26.RSV.preF-based vaccine. Participants will be randomly assigned to different dose levels of Ad26.RSV.preF in the Ad26/protein preF RSV vaccine or to placebo in 3 cohorts. The study vaccine will be administered as a single IM injection.

Cohort	Group	N	Day 1 (Vaccination)
1 (dose-down)	1	50	Ad26.RSV.preF 1×10^{11} vp + RSV preF protein 150 μ g
	2	50	Ad26.RSV.preF 3.3×10^{10} vp + RSV preF protein 150 μ g
	3	50	Ad26.RSV.preF 1.1×10^{10} vp + RSV preF protein 150 μ g
	4	50	Ad26.RSV.preF 3.7×10^9 vp + RSV preF protein 150 μ g
	5	25	Placebo
2 (dose-up)	6	50	Ad26.RSV.preF 1×10^{11} vp + RSV preF protein 150 μ g
	7	50	Ad26.RSV.preF 1.3×10^{11} vp + RSV preF protein 150 μ g
	8	25	Placebo
3 (dose-up)	9	25	Ad26.RSV.preF 1×10^{11} vp + RSV preF protein 150 μ g
	10	50	Ad26.RSV.preF 1.6×10^{11} vp + RSV preF protein 150 μ g
	11	25	Placebo

N = number of participants; vp = viral particles.

The study duration will be approximately 6 months per participant. The end of the study is defined as the last participant's last visit.

An internal Data Review Committee (DRC) will be commissioned for this study, and pre-specified study vaccination pausing rules will be applied to ensure safety of the participants.

In the dose-down cohort (Cohort 1), a target of approximately 225 participants will be randomized in parallel in a 2:2:2:2:1 ratio to 5 groups. In the dose-up Cohort 2, a target of approximately 125 participants will be randomized in parallel in a 2:2:1 ratio to 3 groups. In the dose-up Cohort 3, a target of approximately 100 participants will be randomized in parallel in a 1:2:1 ratio to 3 groups. Cohorts 1 and 2 may be enrolled in parallel, whereas Cohorts 2 and 3 will be enrolled in a staggered manner. A study site will not simultaneously enroll participants in more than one cohort.

Initially, a sentinel group of 5 participants will be enrolled in Cohort 2 in a 2:2:1 ratio to Groups 6 to 8, respectively, before enrolling additional participants (Step 1). A blinded 24-hour postvaccination safety review will be performed by the principal investigator(s) (PI[s]) and sponsor team members (ie, at least the study responsible physician/study responsible scientist). In the absence of any clinical safety concerns, an additional 15 participants will be enrolled in a 2:2:1 ratio (Step 2). After review of the 7-day (Day 8) postvaccination safety data of these 20 participants by the DRC, the remaining participants in the cohort

will be randomized in a 2:2:1 ratio (Step 3). When all participants in Cohort 2 have completed the Day 8 postvaccination visit or discontinued earlier, all available safety data up to at least 7 days after vaccination of all participants in the cohort will be reviewed by the DRC. Based on this review, the sponsor may decide to not initiate enrollment of Cohort 3.

The enrollment of Cohort 3 will be conducted similarly to Cohort 2. Steps 1 and 2 will be performed with a sentinel group of 4 participants and with 12 participants, respectively, both enrolled in a 1:2:1 ratio. After review of the 7-day (Day 8) postvaccination safety data of these 16 participants by the DRC, the remaining participants in the cohort will be randomized in a 1:2:1 ratio.

After vaccination with study vaccine on Day 1, participants will remain under observation at the study site for a minimum of 30 minutes for presence of any acute reactions and solicited events, or longer if deemed necessary by the investigator. Any unsolicited and solicited local (injection site) or systemic AEs will be documented by the study-site personnel following this observation period. Each participant will record solicited local and systemic AEs and body temperature in the participant diary, beginning on the evening of the vaccination day and daily for 7 days after vaccination.

Nasosorption samples using synthetic absorptive matrix (SAM) strips, blood samples to assess humoral and cellular immune responses, and clinical safety laboratory blood samples (Cohorts 2 and 3 only) will be collected. Participant safety throughout the study will further be evaluated via physical examinations and vital signs.

NUMBER OF PARTICIPANTS

A target of approximately 450 participants will be randomly assigned to different dose levels of Ad26.RSV.preF in the Ad26/protein preF RSV vaccine or to placebo in 3 cohorts. In Cohort 1, a target of approximately 225 participants will be randomized, whereas in Cohorts 2 and 3, a target of 125 and 100 participants will be randomized, respectively.

VACCINATION GROUPS AND DURATION

The study duration will be approximately 6 months per participant. Participants in Cohort 1 will be screened on Day 1 (prevaccination), whereas participants in Cohorts 2 and 3 will be screened within 28 days before study vaccine administration to analyze clinical safety laboratory parameters before vaccination. The study further comprises study vaccination (active or placebo) on Day 1 and a 6-month safety and immunogenicity follow-up period.

If a participant meets any of the contraindications to vaccination at the scheduled time for study vaccination on Day 1, enrollment at a later date is permitted at the discretion of the PI and after discussion with the sponsor.

Study Vaccine Administration

On Day 1, participants will receive a single IM injection of study vaccine (ie, the Ad26/protein preF RSV vaccine or placebo) in the deltoid muscle. The injection will occur at the study site. The Ad26/protein preF RSV vaccine is composed of Ad26.RSV.preF (JNJ-64400141) and RSV preF protein (JNJ-64213175). Ad26.RSV.preF will be administered at a dose level ranging from 3.7×10^9 viral particles (vp) to 1.6×10^{11} vp, and RSV preF protein at a constant dose level of 150 μ g. Due to the different dose levels of Ad26.RSV.preF, the injection volumes of the study vaccine may differ between the cohorts. Ad26.RSV.preF and RSV preF protein will be supplied as solutions in separate single-use vials. Placebo will consist of 0.9% saline.

IMMUNOGENICITY EVALUATIONS

Venous blood samples of approximately 10 and 50 mL will be collected for the determination of humoral and cellular immune responses, respectively. Nasosorption samples using SAM strips will be collected for

immunogenicity assessments including, but not limited to, determination of antigen-specific immunoglobulin (IgG and IgA).

Assay	Purpose
Primary and secondary endpoints	
Pre-F protein binding antibody (ELISA)	Analysis of antibodies binding to RSV F protein in prefusion form
RSV A2 neutralization	Analysis of neutralizing antibodies to the A2 strain
IFN- γ (ELISpot)	T-cell IFN- γ responses to RSV F protein peptides
Exploratory endpoints	
Post-F protein binding antibody (ELISA)	Analysis of antibodies binding to RSV F protein in postfusion form
Antigen-specific T-cell immune responses	Analysis of T-cell responses to RSV F protein peptide-stimulated PBMCs (including, but not limited to, CD4 $^{+}$ /CD8 $^{+}$, IL-2, IFN- γ , TNF- α , activation markers and memory) using ICS or CyTOF
RSV strain cross-neutralization	Analysis of cross-neutralizing antibodies to B and/or other A strain(s)
Antibody specificity and functional characterization	Analysis of pre- and post-F antibody specificity by functional assays such as ELISA, competition ELISA, and epitope mapping. Functional characterization of antibodies including, but not limited to, ADCC, ADCP, avidity, immunoglobulin isotype, and functional VNAs to other respiratory viruses
Analysis of nasal antibodies to RSV including, but not limited to, IgA and IgG	Analysis of nasal antibodies binding to RSV F protein in prefusion and/or postfusion form in nasal samples
Adenovirus neutralization assay	Analysis of neutralizing antibodies to Ad26

ADCC = antibody-dependent cell-mediated cytotoxicity; ADCP = antibody-dependent cellular phagocytosis; CD = cluster of differentiation; CyTOF = cytometry by time of flight; ICS = intracellular cytokine staining; IL = interleukin; PBMC = peripheral bone marrow cell; TNF = tumor necrosis factor; VNA = virus neutralization assay.

SAFETY EVALUATIONS

Key safety assessments will include the monitoring of AEs, physical examinations, vital signs, and clinical safety laboratory assessments.

AEs and special reporting situations, whether serious or nonserious, that are related to study procedures or that are related to noninvestigational sponsor products will be reported from the time a signed and dated informed consent form (ICF) is obtained until the end of the study/early withdrawal. All other unsolicited AEs and special reporting situations, whether serious or nonserious, will be reported from the time of vaccination until 28 days after vaccination. All AEs and SAEs leading to discontinuation of the study vaccination (regardless of the causal relationship) are to be reported from the moment of vaccination until completion of the participant's last study-related procedure, which may include contact for safety follow-up. All other SAEs (regardless of the causal relationship) are to be reported from the time of vaccination until the end of the study/early withdrawal.

Any solicited local (injection site) or systemic AEs occurring during the 30-minute postvaccination observation period (or longer if deemed necessary by the investigator) will be documented by the study-site personnel following this observation period. Solicited AEs collected through a participant diary will be recorded from the time of vaccination until 7 days after vaccination.

STATISTICAL METHODS

Sample Size Determination

Immunogenicity (Cohort 1)

The primary objective of Cohort 1 is to explore the dose-response relationship of humoral immune responses (as measured by preF ELISA) induced by different dose levels of the Ad26/protein preF RSV vaccine.

Assuming:

- 10% of exclusions (eg, drop-outs, missing samples, and major protocol deviations impacting immunogenicity data)
- a standard deviation on the \log_2 scale of the preF ELISA of 1.3 on Day 15 and 1.1 on Day 183 for all dose levels
- 4 dose levels

The linear model $\log_2 (\text{preF ELISA}_{\text{timepoint}}) = \text{GMT preF ELISA}_{\text{Ad26/protein preF RSV vaccine (1x10}^{11} \text{vp /150 }\mu\text{g).timepoint}} + \text{slope} \times \# \text{titration steps}$ provides a standard error for the slope of 0.052 on Day 15 and 0.040 on Day 183 with 50 participants per arm. This is deemed sufficient for this exploratory study.

Safety (Cohorts 1, 2, and 3)

Placebo recipients are included for blinding and safety purposes and will provide additional control specimens for immunogenicity assays.

The observation of 0 events (eg, SAEs) is associated with 95% confidence that the true event rate is below the rates specified in the below table for the considered number of participants.

Sample Size	N=25	N=50	N=75
UL 95% one-sided CI	11.3%	5.8%	3.9%

CI = confidence interval; N = number of participants; UL = upper limit.

The table below provides the probability of observing at least one AE in a group of the considered sample size given several true AE rates.

True AE Rate (%)	Probability of Observing at Least One AE in N Participants (%)		
	N=25	N=50	N=75
0.5	12	22	31
1	22	39	53
2.5	47	72	85
10	93	99	100
25	100	100	100
50	100	100	100

N = number of participants.

Analysis Sets

Vaccine assignment will follow the as-treated principle.

The Full Analysis Set (FAS) will include all participants who were randomized and received the study vaccine, regardless of the occurrence of protocol deviations. All safety and participant information analyses will be based on the FAS.

The Per-protocol Immunogenicity (PPI) Set will include all participants who were randomized and received the study vaccine, and for whom immunogenicity data are available, excluding participants with major protocol deviations expecting to impact the immunogenicity outcomes.

The analysis of all immunogenicity endpoints will be based on the PPI set. For key tables, sensitivity immunogenicity analyses might also be performed on the FAS.

Immunogenicity Analyses

No formal statistical testing of immunogenicity data is planned. Immunogenicity data will be analyzed descriptively by cohort and group. In addition, for a selection of tables, data may be pooled over cohorts.

To explore the dose-response relationship between preF ELISA and different dose levels of the Ad26/protein preF RSV vaccine, a linear regression model will be fitted for each timepoint separately, using data of the active groups of Cohort 1, with the log-transformed preF ELISA titers at the considered timepoint as dependent variable, the number of titration steps as independent variable, and the geometric mean titer (GMT) of preF ELISA of the Ad26/protein preF RSV vaccine (1×10^{11} vp/150 μ g) at the considered timepoint as a fixed intercept.

The linear model $\log_2 (preF\ ELISA_{timepoint}) = GMT\ preF\ ELISA_{Ad26/protein\ preF\ RSV\ vaccine\ (1 \times 10^{11}\ vp/150\ \mu g), timepoint} + slope \times \#titration\ steps$ will initially be fitted for the active groups of Cohort 1 but may be extended in a later stage with data of the active groups of Cohorts 2 and 3. A similar model may be fitted as well for other assays.

[figure not shown]
Depending on the model fit, other models (eg, log-linear models or EMAX models) may be explored as well.

Safety Analyses

No formal statistical testing of safety data is planned. Safety data will be analyzed descriptively by cohort and group. In addition, for a selection of tables, data of Cohorts 2 and 3 may be pooled. All safety analyses will be based on the FAS.

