9.3. Populations for Analyses

Vaccine assignment will follow the as-treated principle.

The Full Analysis Set (FAS) will include all participants who were randomized and received the study vaccine, regardless of the occurrence of protocol deviations. All safety and participant information analyses will be based on the FAS.

The Per-protocol Immunogenicity (PPI) Set will include all participants who were randomized and received the study vaccine, and for whom immunogenicity data are available, excluding participants with major protocol deviations expecting to impact the immunogenicity outcomes.

The analysis of all immunogenicity endpoints will be based on the PPI set. For key tables, sensitivity immunogenicity analyses might also be performed on the FAS.

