9.4.3. Safety Analyses

No formal statistical testing of safety data is planned. Safety data will be analyzed descriptively by cohort and group. In addition, for a selection of tables, data of Cohorts 2 and 3 may be pooled. All safety analyses will be based on the FAS.

AEs (Solicited and Unsolicited)

Solicited local (injection site) and systemic AEs will be summarized descriptively. Solicited AEs shown in the tables and listings will be based on the overall assessment of the investigator. The overall frequencies per group as well as frequencies according to severity and duration will be calculated for solicited AEs. In addition, the number and percentages of participants with at least one solicited local (at the injection site) or systemic AE will be presented.

The verbatim terms used in the eCRF by the investigator to report AEs will be coded using the Medical Dictionary for Regulatory Activities (MedDRA). All reported AEs with onset during the active vaccination phase (ie, AEs occurring from the time of vaccination until 28 days after vaccination) and all SAEs will be included in the analysis. For each AE, the number and percentage of participants who experience at least one occurrence of the given event will be summarized by group. Frequency tables of unsolicited AEs, separately for all and study vaccine-related, will be presented by system organ class and preferred term.

Summaries, listings, datasets, or participant narratives may be provided, as appropriate, for those participants who die, who discontinue study vaccination due to an AE, or who experience a severe AE or an SAE.

Summaries and/or listings may be provided separately for AEs with onset outside the above defined timeframe (ie, beyond 28 days after vaccination).

Clinical Laboratory Tests (Cohorts 2 and 3 only)

Laboratory abnormalities will be determined according to the FDA toxicity grading tables (Section 10.2, Appendix 2) or, for tests for which no grades are available, in accordance with the normal ranges of the clinical laboratory. Any laboratory value shown as a "graded" value in the FDA table that is within central laboratory normal ranges will not be graded for severity.

Vital Signs

A tabulation of the distribution of body temperatures per half degree intervals will be provided. For systolic and diastolic blood pressure and heart and respiratory rate, the percentage of participants with values beyond clinically relevant limits will be summarized.

Physical Examination

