### 2.3.1. Full Analysis (FA) set

The FA set will include all participants who were randomized and received the study vaccine, regardless of the occurrence of protocol deviations. All safety and participant information analyses will be based on the FA set.

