## 3. INTERIM ANALYSIS AND DATA MONITORING COMMITTEE REVIEW

An internal Data Review Committee (DRC) will be commissioned for this study to discuss any safety issues and any situation meeting a specific study vaccination pausing rule (CTP Sections 9.6 and 7.3). Planned data reviews of the DRC are specified in CTP Section 4.1. The role and responsibilities of the internal DRC are detailed in the DRC Charter. The DRC analyses will follow the same statistical methods described in this SAP. A separate DPS document has been provided to describe specifications of individual tables, listings and figures to be generated in each DRC analysis.

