### 4.2. Disposition Information

The number and percentage will be tabulated for subjects that were:

- Screened
- not randomized, not vaccinated
- not randomized but vaccinated
- randomized not vaccinated
- randomized and vaccinated (subjects in the FA set)
- in the PPI set

Number and percentage of subjects who discontinued the study together with the reason(s) for discontinuation will also be tabulated.

The number and percentage of subjects per study phase and period will also be tabulated.

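### The only set used for safety requires randomization, so someone vaccinated without being randomized would be missing from the safety summary tables despite exposure

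*Protocol*

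**What the plan says.** The Protocol synopsis and Section 9.3 define the Full Analysis Set by two conditions, randomization and receipt of study vaccine: the set "will include all participants who were randomized and received the study vaccine, regardless of the occurrence of protocol deviations". SAP 2.3.1 does the same: "The FA set will include all participants who were randomized and received the study vaccine, regardless of the occurrence of protocol deviations".

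The scope is just as plain. Protocol 9.3: "All safety and participant information analyses will be based on the FAS". Protocol 9.4.3: "All safety analyses will be based on the FAS". SAP 2.3.1: "All safety and participant information analyses will be based on the FA set". SAP Section 6 takes the denominator of each safety percentage from the analysis set. Neither document defines another safety set.

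SAP 4.2 lists disposition categories. One is "not randomized but vaccinated"; a separate one is "randomized and vaccinated (subjects in the FA set". The first group is therefore outside the set by the SAP's own labelling.

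Protocol 9.4.3 also says that all AEs with onset in the active phase, and all SAEs, go into the analysis. SAP 6.1.1 says SAEs are presented throughout the study.

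On the DRC, SAP Section 3 says: "The DRC analyses will follow the same statistical methods described in this SAP". It names no analysis set. Protocol 9.6 has the DRC review all safety data collected in Cohorts 2 and 3 up to stated cut-offs.

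**The concern.** Whether an exposed person's adverse events count should depend on exposure. Under the stated definition it also depends on randomization. A person vaccinated without being randomized would be counted once, in disposition, and then be absent from every numerator and denominator of the safety summaries. The remark that protocol deviations do not matter gives no relief, because it applies to people who already meet both conditions.

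Safety is the primary objective of Cohorts 2 and 3, where 1.3×10^11 and 1.6×10^11 vp are given for the first time, in groups of 50. The protocol describes its safety precision through what can be concluded from zero events (Table 5). Dropping one exposed person with an event could turn one observed event into none.

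**Working it through.** **Step 1. Follow one person through the rules.** Take someone who received study vaccine but was not randomized.

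| Rule | Result for this person |
|---|---|
| FAS/FA set (Protocol synopsis, 9.3; SAP 2.3.1) | Out: the randomization condition fails |
| Set for safety (Protocol 9.3, 9.4.3; SAP 2.3.1) | FAS only, so out |
| Safety denominators (SAP 6) | Out |
| Disposition (SAP 4.2) | Counted in a row of its own |
| All SAEs in the analysis (Protocol 9.4.3) | In, which cannot be met if the FAS is the only set |
| As-treated principle (Protocol 9.3; SAP 2.3) | Decides the vaccine group of a set member; does not decide membership |

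SAP Section 4 contains a related slip. It bases subject information on the FA set, yet several disposition rows in 4.2 describe people who cannot be in that set.

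**Step 2. Reproduce the plan's own figures.** Protocol Table 5 gives one-sided 95% upper limits for zero events. The exact limit is 1 − 0.05^(1/N):
- N=25: 11.29% (table 11.3%)
- N=50: 5.82% (table 5.8%)
- N=75: 3.92% (table 3.9%)

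All three agree.

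**Step 3. Size of the effect of one omitted person.** Assume one vaccinated, non-randomized person belongs with a group of n by vaccine received, and nobody else in the group has the event. The exact (Clopper-Pearson) one-sided 95% upper limit for x events in m people is the 0.95 quantile of Beta(x+1, m−x).

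| n | Reported, person omitted: 0/n | Person counted, with the event: 1/(n+1) | Person counted, no event: 0/(n+1) |
|---|---|---|---|
| 50 | 0/50, limit 5.82% | 1/51 = 1.96%, limit Beta(0.95; 2, 50) = 8.97% | 0/51, limit 5.70% |
| 25 | 0/25, limit 11.29% | 1/26 = 3.85%, limit Beta(0.95; 2, 25) = 16.98% | 0/26, limit 10.88% |

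Protocol Table 2 gives N=50 to both new-dose groups (Groups 7 and 10). The N=25 groups receive placebo or 1×10^11 vp, so the second row does not describe the new doses.

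**Step 4. What does not pass through the FAS.** SAE reporting within 24 hours (Protocol 8.3.1), SUSAR reporting (8.3.4), special reporting situations such as medication errors (Appendix 3) and the pausing rules (7.3) are all written for participants, with no reference to an analysis set.

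**The case against.** The strongest reply is that little is lost in practice. The IWRS code dictates the group (Protocol 6.3) and syringes are prepared and labelled per participant (6.2), so vaccination without randomization should hardly ever happen. If it did, the disposition row would show it, and the events would still be collected, reported and subject to the pausing rules. The 5.8% versus 9.0% contrast needs a rare error, an event in that very person, and no other event in the group. Table 5 is also a planning table; the SAP plans counts and percentages, not these limits. All of this stands, and it keeps the point small. It does not remove the gap in the summary tables.

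Some stronger readings are tempting but not supported:

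- *The DRC would not see the case.* Protocol 4.1 and 9.6 give it all available or collected safety data, and 7.3 sends it all deaths. SAP Section 3 carries over statistical methods without naming a set. The DRC charter and its table specifications are separate documents, so one can say only that DRC tables would omit the person if they use the FA set.
- *The sentinel review would lose a large share of its participants.* That 24-hour review is done by the PI(s) and sponsor team (Protocol 4.1). It is not an FAS table, and a non-randomized person would be additional to the 5 or 4 sentinels.
- *The definition contradicts the as-treated principle.* That principle governs which vaccine a set member is analysed under, not who is in the set.
- *The SAP expects this error.* Its four rows cross randomized or not with vaccinated or not. Listing every cell shows that the case was considered, not that it is anticipated.

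**Conclusion.** The point holds as a gap in the definition of the safety population. By the text of both documents, a vaccinated but non-randomized participant is left out of the summary AE, SAE, laboratory and vital-sign tables, which does not fit the statement in Protocol 9.4.3 that all SAEs are included.

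The expected effect is small. The documents give no frequency for such cases, and central randomization should make them rare. The worst-case size for a new-dose group is 0/50 (upper limit 5.8%) reported in place of 1/51 (9.0%), assuming one such person who has the group's only event. Without an event the limit would be 5.7%. This is an inexpensive improvement to the wording; nothing here suggests that events would go unreported or that safety oversight would fail.

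**What to change.** Define a safety set in the Protocol synopsis and 9.3 and in SAP 2.3: all participants who received study vaccine, randomized or not, analysed by vaccine received. Name it wherever the FAS or FA set is now named for safety (Protocol synopsis, 9.3, 9.4.3; SAP 2.3.1 and Section 6), and state that the DRC tables use it. Footnote any non-randomized person. Because placebo and 1×10^11 vp occur in all three cohorts, also say how that person's cohort is set; the cohort then enrolling at the site would serve, since Protocol 4.1 has a site enroll one cohort at a time. Keep randomization plus vaccination as the condition for the PPI set and for the immunogenicity sensitivity analyses on the FAS.

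The cost is one extra analysis set and derivation flag, matching edits at each of those places, and the possibility of a non-randomized person in a by-group safety denominator. If the sponsor prefers by-group tables restricted to randomized participants, a separate listing and description of vaccinated non-randomized participants would be a weaker alternative: it makes their events visible but leaves them out of the rates.
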